4.6 Stratification Factors and Treatment Assignments

The factors listed below will be used as stratification factors. After a patient has been registered, the values of the stratification factors will be recorded, and the patient will be assigned to either hypofractionated or standard radiation dosing using the Pocock and Simon dynamic allocation

procedure, which balances the marginal distributions of the stratification factors between the treatment groups (Pocock-Simon).

Patients will be stratified before randomization based on planned intent for:

- autologous (+/- implant) vs.
- implant only breast reconstruction.
- Patients will be stratified before randomization based on:
 - immediate reconstruction vs.
 - planned for delayed breast reconstruction (**includes patients who have had no reconstruction or only a temporary expander placed at time of randomization.**)
- ** Patients undergoing immediate reconstruction will already have completed reconstruction at the time of randomization.
- *** Patients who have a tissue expander placed at the time of mastectomy and then have a delayed final reconstruction will be classified as delayed for purposes of stratification and randomization.

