7.2 Breast Reconstruction

Reconstruction of the breast may occur before or after radiation but must be completed within 18 months of finishing radiation therapy, unless medically contraindicated.

A fluid filled tissue expander may be placed before or after radiation and maybe inflated or deflated for radiation. No change in volume of the expander may occur after radiation simulation and before the last fraction of PMRT. Air tissue expanders are not recommended and if utilized, must be deflated for radiation simulation and treatment delivery due to the difficulty with dose calculation and reporting at air/tissue interfaces. Additionally, the tissue expander is part of the radiation target volume, which must receive the prescription dose which is not possible in air.

Plastic surgeon may use any combination of allograft, saline, silicone, or autologous tissue flap for reconstruction. The method and timing of reconstruction must be documented on the eCRF.

Reconstruction intent must be stated at the time of registration, and may include the following:

- Implant only reconstruction before radiation
- Autologous reconstruction before radiation (with or without implant)
- Temporary expander placement at the time of mastectomy, radiation, with subsequent delayed reconstruction with implant only
- Temporary expander placement at the time of mastectomy, radiation, with subsequent delayed reconstruction with autologous tissue with or without implant
- Mastectomy without tissue expander, followed by radiation, with subsequent delayed reconstruction with implant, only.
- Mastectomy without tissue expander, followed by radiation with subsequent delayed reconstruction with autologous tissue with or without implant

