10.0 MEASUREMENT OF EFFECT**10.1 Ipsilateral Reconstruction Complications**

Reconstruction complications will be defined as:

- Capsular contracture (Baker Grade III or IV only)
- Complete failure of the implant/skin flap
- Unplanned admission for reconstruction related issue(s) including but not limited to infection, wound healing complication or pain
- Unplanned return to the operating room for recon related issue including but not limited to infection, prosthesis exposure, failed reconstruction, implant removal, wound healing complications or contracture management

Note: Complications related to the contralateral breast will be collected but will not count towards the assessment of the primary endpoint, ipsilateral breast complications will be counted towards the primary endpoint.

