12.2 Sample Size, Accrual Time and Study Duration

Our target sample size will be 792 evaluable patients (396 in each arm). To account for 10% drop-out due to cancellations or protocol deviations, our target accrual is 880 patients (440 per arm) (90% of 880 is 792).

The study design is a randomized, un-blinded, non-inferiority trial. It is assumed that the two-year breast reconstruction complication rate for the control arm (Arm 1: standard fractions) is 25%. Other assumptions for the sample size determination include:

- α (one-sided) = 0.025
- power = 90%
- non-inferiority margin: the absolute increase in the proportion of patients who experience
- a breast reconstruction complication within two-years is 10% above that of the control arm.
- one interim analysis (when 30% of the information is obtained) for futility

Under an alternative hypothesis that the true rates in the two arms are equal, a sample size of 792 (396 per arm) evaluable patients would give us 90% power to reject the null hypothesis of inferiority. The final analysis will take place after all patients have reached two years post-radiation. The anticipated accrual period is approximately 30 months, and the total study duration is approximately 60 months. We anticipate being able to accrue approximately 30 patients per month based on our best estimate extrapolated from recently closed intact breast trials looking at similar fractionations. It should be noted that if we instead assumed a complication rate of 50% in the control arm (the most statistically conservative, in terms of sample size), the above sample size would still give us approximately 80% power to reject the null hypothesis of inferiority (again with one-sided α of 0.025).

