Simulation studies of 10,000 clinical trials are conducted for the proposed group sequential design. The probabilities of early stopping (at the interim analysis) and empirical powers for various scenarios are summarized in the following table. Of particular interest, assuming that the two-year breast reconstruction complication rate is 25% for the control arm (Arm 1: conventional PMRT) and 35% for the hypofractionated PMRT (Arm 2), where the Arm 2 treatment is inferior to Arm 1, there is a 14.45% chance of stopping the trial early to conclude that hypofractionated PMRT is inferior. In another scenario where the complication rate of the conventional PMRT is 25% and that of hypofractionated is 25%, where the Arm 2 treatment is truly non-inferior to Arm 1, the likelihood of stopping early to conclude inferiority is 0.24% and the likelihood of the trial concluding that hypofractionated PMRT is non-inferior to conventional one is 90.84% (power).

Reconstruction complication rate		Interim analysis conclusion		Early stopping	Final analysis conclusion		Rejection (of H_0) rate
Conventional	Hypofractionated	Noninferior	Inferior		Noninferior	Inferior	
25%	35%	0.00%	14.45%	14.45%	2.37%	83.18%	2.37%
	30%	0.00%	2.86%	2.86%	34.51%	62.63%	34.51%
	25%	0.00%	0.24%	0.24%	90.84%	8.92%	90.84%

It should be noted that the primary analyses will be an intent-to-treat analysis where all patients randomized will be included in the analysis and will be analyzed based on the arm they were randomized to regardless of actual radiation schedule received. This analysis will not be stratified. Due to the random treatment assignment with stratification for the timing of reconstruction and type of reconstruction, it is expected that the baseline patient characteristics, including the planned reconstruction procedures, are roughly balanced across the two treatment arms. A sensitivity analysis stratified by timing and type of reconstruction surgery will be conducted.

The frequency and the proportion of patients who enrolled in the trial prior to reconstruction surgery who did not receive the surgery within 18 months of radiation as specified in the eligibility criteria will be summarized separately by arm. A secondary analysis excluding these patients will be conducted.

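### The secondary analysis that drops patients not reconstructed by 18 months makes no exception for those who already had a complication, so it can delete primary-endpoint events

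*Combined protocol and SAP*

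**What the plan says.** The primary analysis in Section 12.3.2 is by intention to treat and includes everyone randomised. The same section then singles out "patients who enrolled in the trial prior to reconstruction surgery who did not receive the surgery within 18 months of radiation". Their number and proportion are to be summarised by arm, and then: "A secondary analysis excluding these patients will be conducted". The reason for non-reconstruction plays no part in the rule, and neither does a prior complication.

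Three other sections determine who falls under it.

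- Section 4.6 treats expander-only patients as not yet reconstructed: "Patients who have a tissue expander placed at the time of mastectomy and then have a delayed final reconstruction will be classified as delayed".
- Section 10.1 counts, among other things, "Unplanned return to the operating room for recon related issue including but not limited to infection, prosthesis exposure, failed reconstruction, implant removal", and also unplanned admission for a reconstruction-related problem. The only expander-specific exemption is in Section 9.2.3, for a contracture corrected at exchange.
- Section 7.2 says reconstruction "must be completed within 18 months of finishing radiation therapy, unless medically contraindicated". That medical exception is not carried into the exclusion in Section 12.3.2.

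**The concern.** A planned-delayed patient with an expander can lose it to infection or exposure after radiation. If the removal needs an unplanned return to theatre or an unplanned admission, she has a primary-endpoint event. If her final reconstruction is then abandoned or pushed past 18 months, she also meets the exclusion, and both she and her event leave the secondary analysis.

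The exclusion therefore conditions on a state that arises after randomisation and that the endpoint itself can cause. A natural use of this analysis is to ask whether patients who were never reconstructed, and so had little opportunity for an event, pulled the arms together in the intention-to-treat comparison. That matters in a non-inferiority trial. An analysis that can also remove serious failures does not answer that question cleanly, and its agreement with the primary result could reassure wrongly.

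**Working it through.** **Design figures first.** Inputs from Section 12.2: 25% in both arms under the alternative, a 10-point margin, "α (one-sided) = 0.025", 90% power. With the unpooled variance of the plan's own Z statistic:

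n per arm = (1.960 + 1.282)² × (2 × 0.25 × 0.75) / 0.10² = 394.03, rounded up to 395, against the stated 396.

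Power at 396 per arm is 90.1%. At 25% v 35%, exactly at the margin, the chance of concluding non-inferiority is 2.5%. The plan's figures reproduce, so the same Z statistic is used below, in a single look.

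**Effect of the exclusion.** For one arm, let p be the true two-year rate, e the share excluded after an event, and b the share excluded without one. Then

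observed rate = (p − e) / (1 − e − b), on 396 × (1 − e − b) patients.

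For fixed p and b this falls as e rises, because its derivative in e has the sign of p + b − 1, which is negative here. The comparison between arms depends on how much e differs and on b.

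Chance of non-inferiority = Φ[(0.10 − difference) / SE − 1.96], with SE the unpooled standard error on the reduced arms.

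**Illustrations at 25% v 35%.** The values of e and b are assumptions; the documents give neither.

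| e, Arm 1 v Arm 2 | b per arm | Observed rates | Difference | Chance of non-inferiority |
|---|---|---|---|---|
| none | 0 | 25.0% v 35.0% | 10.0 points | 2.5% |
| 5% v 5% | 0 | 21.1% v 31.6% | 10.5 points | 1.7% |
| 5% v 7% | 10% | 23.5% v 33.7% | 10.2 points | 2.2% |
| 5% v 7.5% | 0 | 21.1% v 29.7% | 8.7 points | 6.1% |
| 5% v 10% | 0 | 21.1% v 27.8% | 6.7 points | 17.7% |
| 5% v 10% | 10% | 23.5% v 31.3% | 7.7 points | 9.6% |
| 5% v 15% | 0 | 21.1% v 23.5% | 2.5 points | 67.3% |
| 5% v 15% | 10% | 23.5% v 26.7% | 3.1 points | 51.1% |

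For example, 5% v 10% with b = 0: (0.25 − 0.05)/0.95 = 0.2105 on 376 patients and (0.35 − 0.10)/0.90 = 0.2778 on 356. The SE is 0.0317, and (0.10 − 0.0673)/0.0317 − 1.96 = −0.93, which gives 17.7%.

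**Where the direction turns.** With e = 5% in Arm 1, the difference falls below 10 points only once the excess in Arm 2 passes about 0.7 points (b = 0), 1.5 points (b = 5%) or 2.3 points (b = 10%). Below that, the smaller denominators widen the gap slightly.

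**The case against.** The strongest reply has four parts.

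- **It is a supporting analysis.** The non-inferiority decision rests on all randomised patients, and no decision rule attaches to the secondary analysis. This stands. A reader might infer that the trial's conclusion is at risk; the documents do not support that, because every event stays in the primary comparison.
- **An imbalance would be visible.** Section 12.3.2 already requires the number and proportion of these patients by arm, so an excess as large as 5% v 15% would show. This stands in part: the summary is not split by prior event or by reason, so a reader could see that more patients were dropped but not that their events went with them.
- **The direction is not fixed.** A reader might infer that the analysis always favours the arm with more failures. It does not. The failures must remain unreconstructed at 18 months, their excess must be large enough, and event-free exclusions must be similar by arm. The 5% v 7% row shows more failures in Arm 2 and no advantage to it.
- **Other analyses bear on dilution.** A reader might also infer that this is the plan's only check on it. The documents state no purpose for the analysis. Section 12.4.1 compares the arms within type-and-timing subgroups, and under Section 4.6 patients with immediate reconstruction have completed it by randomisation. The immediate subgroups therefore contain no never-reconstructed patients, although they say nothing about planned-delayed patients.

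The event status of an expander loss rests mainly on the reoperation and admission components, since Section 10.1 does not name expanders under complete failure. That narrows which losses count but does not remove the overlap.

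**Conclusion.** The point holds in a limited form. As written, the exclusion in Section 12.3.2 can delete primary-endpoint events, because planned-delayed expander patients are covered by it and an unplanned expander removal can already be an event. When unsalvaged failures are sufficiently more common in one arm and event-free exclusions are similar, that arm looks better than it is. With small or no excess the gap can widen slightly instead.

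The documents do not fix the size. The nearest figure is the 18% failure rate at 3.8 years in a 99-patient immediate-expander series in Section 1.2, which does not say how many patients stayed unreconstructed. Under the assumed 5% v 10%, the chance of a misleading non-inferiority result in this analysis is about 18%, or about 10% with a further 10% of event-free exclusions per arm, against 2.5%. The 5% v 15% case (67%) puts the whole 10-point excess into unsalvaged failures and is an extreme bound, not a forecast. The change is worth making because it is cheap, not because the primary result is in doubt.

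**What to change.** Reword the exclusion in Section 12.3.2 as follows.

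- Keep in the secondary analysis, as events, all patients with a Section 10.1 event before the 18-month point.
- Keep event-free patients who had an expander placed, since they were at risk. Dropping them while keeping events would itself depend on outcome: with true rates of 25% in both arms and event-free exclusions of 5% v 10%, the observed rates become 0.25/0.95 = 26.3% and 0.25/0.90 = 27.8%, a spurious 1.5 points against Arm 2.
- Exclude only planned-delayed patients who had neither an expander nor reconstruction by 18 months, and so were not at risk up to then.
- Report the number not reconstructed by arm, split by prior Section 10.1 event or none, and by reason where the notes record it.
- Label the result a sensitivity analysis, because it still conditions on a post-randomisation state.

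The cost is a short amendment to Section 12.3.2, best fixed before outcomes by arm are known, with no extra patients. The secondary result may become less favourable. The operative and complication notes required by Section 6.1.4 should supply the split by prior event. That section names no record of patient choice, or of a contraindication without a complication, so a full table of reasons may need an added field.

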12.4 Supplementary/Secondary Analysis Plans

12.4.1 Secondary Objectives

Incidence of acute and late radiation complications based on CTCAE 4.0 toxicity. The proportion of patients with acute or late radiation complications, will be estimated separately by treatment arm and will be compared across the two arms using two-sample test of proportions (Z test) with a two-sided alternative.

Local and local regional recurrence rate: The cumulative incidence of local and local regional recurrence will be estimated separately by treatment arm using the cumulative incidence function treating death as the competing risk and will be compared using Gray's test. In addition, local and local regional recurrence free survival will be summarized for each arm using the Kaplan-Meier estimators, and will be compared using a log rank test.

Reconstruction complication rates based on reconstruction method (autologous +/- implant vs. implant only) and timing of reconstruction received (immediate vs. intent for delayed): Between-arm differences in reconstruction complication rates will be assessed separately within each of the six subgroups based on type and timing of reconstruction. Between-arm differences in complication rates will also be assessed within the two broader subgroups of patients who receive implant only and those who receive autologous based reconstruction. Within each subgroup, the comparison will be done using a two-sample Z test of proportions with a two-sided alternative as described for the primary analysis in Section 12.3.2.

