1.2 Baseline Toxicity from PMRT

In reviewing toxicity data from previous PMRT trials, the Vancouver BC trial reported 9% arm lymphedema (4% needing intervention) and 0.6% symptomatic pulmonary fibrosis. [23]. There was no assessment of cosmesis or reconstruction complications reported in the Danish or Vancouver BC PMRT trials, or the PMRT participants of the UK Start trials. Although not a trial looking at mastectomy patients, the NCIC MA.20, revealed a 7% risk of grade 2 or greater lymphedema in the regional nodal radiation group treated with standard fractionation. [28] With approximately 25% of the Start trial patients undergoing mastectomy, the 5 yr. toxicity data from the hypofractionation arm of 40Gy in 15 fractions in the Start B trial reported the following:

Symptomatic rib fracture	2%
Lung fibrosis	1.7%
Ischemic heart disease	1.5%
Brachial plexopathy	0%
Breast edema	5%
Telangiectasia	1.8%
Arm stiffness	3%
Arm Lymphedema	3%

Based on this information, we feel that a reasonable expected combined grade 2 or greater non-acute toxicity rate would be 7-10%, a conservative estimate as many trials (including NCIC MA.20) have concluded that the risk of grade 2 lymphedema alone to be at least this high with regional nodal RT. In the next section, the 2014 updated analysis of Start A and B is discussed with results suggesting that toxicity from hypofractionation may actually be superior to conventional fractionation.

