9.1 Routine Adverse Event Reporting

Adverse event data collection and reporting, which are required as part of every clinical trial are done to ensure the safety of patients enrolled in the studies as well as those who will enroll in future studies using similar agents. Adverse events are reported in a routine manner at scheduled times according to the study calendar in Section 5.0. For this trial, Solicited Adverse Event Solicited form is used for routine AE reporting in Rave.

Acute Adverse Events: Acute adverse events, will be scored per CTCAE 4.0 regardless of attribution. Attribution will however be collected for separate analysis.

Late Radiation Adverse Events: Late radiation complications will be defined as those that are present ≥ 6 months after the final dose of radiation and include CTCAE 4.0 grade 3+:

9.2 Solicited Adverse Events:

The following adverse events are considered "expected" and their presence/absence should be solicited, and severity graded, at baseline and for each cycle of treatment.

9.2.1 Radiation Therapy Complications:

CTCAE v4.0 Term	CTCAE v4.0 System Organ Class (SOC)
Fibrosis, deep connective tissue	Musculoskeletal and connective tissue disorders
Superficial soft tissue fibrosis	Musculoskeletal and connective tissue disorders
Chest wall pain	Musculoskeletal and connective tissue disorders
Joint range of motion decreased	Musculoskeletal and connective tissue disorders
Wound Infection	Infections and infestations
Fatigue	General disorders and administration site conditions
Dermatitis radiation	Injury, poisoning and procedural complications
Wound complication	Injury, poisoning and procedural complications
Wound dehiscence	Injury, poisoning and procedural complications
Lymphedema	Vascular disorders
Telangiectasia	Skin and subcutaneous tissue disorders
Hypothyroidism	Endocrine Disorders
Myocardial Infarction	Cardiac disorders
Cardiac disorders – Other specify*	Cardiac disorders
Pulmonary fibrosis	Respiratory, thoracic and mediastinal disorders
Brachial Plexopathy	Nervous system disorders
Peripheral motor neuropathy	Nervous system disorders
Peripheral sensory neuropathy	Nervous system disorders
Treatment related secondary malignancy	Neoplasms benign, malignant and unspecified (including cysts and polyps)

* Specific cardiac events, if and when they occur will be recorded on the Adverse Events: Other form.

9.2.2 Non CTCAE RT Associated Complications:

- a) Shoulder stiffness (occasional) (Grade 1-3)

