10.2 Acute and Late Radiation Complications

Acute Adverse Events: Acute adverse events, will be scored per CTCAE 4.0 regardless of attribution. Attribution will however be collected for separate analysis.

Late Radiation Adverse Events: Late radiation complications will be defined as those that are present ≥ 6 months after the final dose of radiation and include CTCAE 4.0 grade 3+:

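### The CTCAE acute/late comparison in 12.4.1 is less sensitive than the collected grades allow: late events are cut at grade 3+, and acute events have no stated grade cut or baseline rule

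*Combined protocol and SAP*

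**What the plan says.** Section 12.4.1 gives the analysis in one sentence: "The proportion of patients with acute or late radiation complications, will be estimated separately by treatment arm", to be "compared across the two arms using two-sample test of proportions (Z test) with a two-sided alternative". It names no grade, time window, baseline rule or significance level, and it does not say whether acute and late complications are two endpoints or one.

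The definitions are in section 10.2 and repeated in 9.1:

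- **Acute:** "Acute adverse events, will be scored per CTCAE 4.0 regardless of attribution", followed by "Attribution will however be collected for separate analysis". No grade threshold or end of window is given, and 12.4.1 does not describe the separate analysis.
- **Late:** events "present ≥ 6 months after the final dose of radiation and include CTCAE 4.0 grade 3" or higher. The sentence ends in a colon with no list after it.

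Section 1.2 gives the expected level of late toxicity: "a reasonable expected combined grade 2 or greater non-acute toxicity rate would be 7-10" per cent. Section 9.2 has the solicited terms "severity graded, at baseline and for each cycle of treatment", and the calendar in section 5.0 schedules adverse event assessment before radiation and at visits up to 5 years.

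**The concern.** The late cut drops grade 2, the level at which section 1.2 expects the toxicity. Grade 2 fibrosis, pulmonary toxicity or plexopathy would not count. Section 1.0 makes the safety of treating nodal volumes, where it notes the brachial plexus lies, one of the trial's two questions.

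The acute endpoint has the opposite difficulty. The solicited list includes radiation dermatitis, fatigue and chest wall pain. Some of these may already be present after mastectomy and chemotherapy. With no grade cut and no use of the baseline grade, the proportion with an event could be high in both arms.

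Sharper rules appear elsewhere in the protocol. The stopping rule in 12.7.2 requires at least possible attribution, and its grade 3+ limb excludes acute dermatitis. The arm-volume endpoint in 12.4.3 is a change from the pre-radiation value.

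Section 1.6 hypothesises a similar rate of treatment toxicity. A two-sided difference test with no margin and low power is likely to give a non-significant result, and that could be read as confirming the hypothesis.

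**Working it through.** **Inputs.** Section 12.2: "Our target sample size will be 792 evaluable patients (396 in each arm"). Section 1.2: 7-10% late toxicity at grade 2+. Section 12.4.1: two-sided Z test. Assumed: alpha 0.05, because none is stated; all grade 3+ late rates; all acute rates.

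**The plan's own figure.** For the primary endpoint, n = 2 × 0.25 × 0.75 × (1.960 + 1.282)² / 0.10² ≈ 394.03, so 395 per arm (stated 396). Power at 396 is Φ(0.10 / √(2 × 0.25 × 0.75 / 396) − 1.960) = Φ(3.250 − 1.960) = 90.1% (stated 90%). Also 792 / 0.9 = 880. These agree. The plan gives no power for the toxicity comparison.

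**Formula for what follows.** Power = Φ(|p1 − p2| / SE − 1.960), with SE = √([p1(1 − p1) + p2(1 − p2)] / 396).

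**Late events, power to detect a doubling**

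| Cut | Rates | SE | Difference / SE | Power |
|---|---|---|---|---|
| Grade 2+ (section 1.2) | 7% v 14% | 0.0216 | 3.23 | 90% |
| Grade 2+ (section 1.2) | 10% v 20% | 0.0251 | 3.98 | 98% |
| Grade 3+ (assumed) | 1% v 2% | 0.0086 | 1.16 | 21% |
| Grade 3+ (assumed) | 2% v 4% | 0.0121 | 1.65 | 38% |
| Grade 3+ (assumed) | 3% v 6% | 0.0147 | 2.04 | 53% |
| Grade 3+ (assumed) | 4% v 8% | 0.0168 | 2.38 | 66% |

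With 80% power the smallest detectable rise is about 7% to 13.0% or 10% to 16.8% at grade 2+. At grade 3+ it is about 1% to 4.2% or 2% to 5.9%, which is three- to four-fold. For a 1.5-fold rise, grade 2+ itself has only 41.5% (7% v 10.5%) to 56.9% (10% v 15%).

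**Acute events, all rates assumed.** Take one odds ratio of 0.67 at every cut. The second rate is then q = o / (1 + o), with o = 0.67 × p / (1 − p).

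- Any grade, 90%: o = 6.03, q = 85.8%, power 45%.
- Any grade, 95%: o = 12.73, q = 92.7%, power 27%.
- Any grade, 98%: o = 32.83, q = 97.0%, power 14%.
- Grade 2+, 40%: q = 30.9%, power 77%. At 50%: q = 40.1%, power 80%.
- Grade 3+, 5%: q = 3.4%, power 20%.

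**Baseline events.** Suppose 80% of patients already have a listed event and new onset is 40% v 30%. The observed rates become 0.8 + 0.2 × 0.4 = 88% and 0.8 + 0.2 × 0.3 = 86%. Power falls from 84% to 13%.

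**Acute and late combined.** Suppose 80% in both arms have an acute event, independent of late events. Late grade 3+ of 2% v 6% has 82% power alone. Combined, the rates are 0.8 + 0.2 × 0.02 = 80.4% and 0.8 + 0.2 × 0.06 = 81.2%. Difference / SE is 0.29 and power, counting both tails, is about 6%, close to alpha.

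**The case against.** The case against is substantial, and several parts of it stand.

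- **Any grade, near ceiling.** A reader might infer that the plan counts grade 1 events and that almost every patient will score. The documents do not say so. They state no acute cut and no any-grade rate, and the loss depends on the rate: 45% power at 90% against 14% at 98%.
- **Any cause.** Attribution is collected and a separate analysis is foreseen. The gap is only that 12.4.1 does not specify it.
- **Baseline.** A reader might take the missing baseline rule as bias. In a randomised comparison it dilutes a difference but does not bias the test.
- **Late cut.** The grade 3+ sentence is unfinished, possibly because text was lost in conversion. Grade 3+ is the likely reading, not a certain one. The 7-10% in section 1.2 is background and is not tied to a power calculation.
- **Coverage elsewhere.** A reader might conclude that the trial's safety assessment as a whole is insensitive. It is not: reconstruction complications are the powered primary endpoint. Arm lymphedema, which section 1.2 says may alone account for the 7-10%, is tested in 12.4.3 as change from pre-radiation volume. Cosmesis is tested in 12.4.2, and lymphedema symptoms in 12.4.4. Plexopathy events are recorded to 15 years under section 5.0.
- **Grade 2 in an open-label trial** depends more on judgement, so replacing grade 3+ outright would be a trade-off.

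None of this supplies a between-arm test of fibrosis, pulmonary or other grade 2 late toxicity, and section 12.4 states no analysis of the plexopathy events.

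**Conclusion.** The concern holds for the CTCAE acute/late comparison only. The firm part rests on the documents: the late definition is at grade 3+ while the expected combined rate is for grade 2+; acute events have no cut, window or baseline rule; and it is unstated whether acute and late are tested separately.

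For late events, power to detect a doubling is 90-98% at the protocol's grade 2+ rates, against 21-66% at an assumed 1-4% grade 3+ rate. This supposes the same relative effect at both cuts. In absolute terms grade 3+ detects a smaller gap (about 3 to 4 points against 6 to 7), so the loss is on the relative scale.

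The acute and combined figures are illustrations from assumed rates. They show what an unspecified endpoint could cost, not what it will cost.

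**What to change.** In 10.2 (with the matching text in 9.1) and 12.4.1:

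1. Test acute and late complications separately, and state the acute window.
2. Count solicited events that are new or worse than the patient's pre-radiation grade.
3. Analyse late events at grade 2+ alongside the existing grade 3+ definition, and complete the unfinished sentence.
4. Analyse acute events at grade 2+ and at grade 3+, and specify the attribution analysis.
5. Tabulate brachial plexopathy of any grade by arm. With 0% in the hypofractionated arm cited in section 1.2, a test would add little.

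The cost is wording and programming. One point needs confirming: 9.2 speaks of grading at baseline and each treatment cycle, and the late form in 9.3 takes only grade 3+. The sponsor should check that the solicited form, which 9.1 ties to the study calendar, captures grade 2 at follow-up visits. The downside is the subjectivity of grade 2 grading in an open-label trial, which is why grade 3+ stays and both are reported.
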